- 3) Population mean levels of AEE are negatively related to population mean levels of obesity/relative weight.
- 4) Adipocytokines (e.g., adiponectin and leptin) and hormones (e.g., ghrelin) influence weight regulation and insulin sensitivity and interact with AEE.
- 5) Heavy metals, such as arsenic, mercury, lead and cadmium, are positively associated with obesity and markers of diabetes and CVD risk.
- 6) Human gut and oral microbiome and plasma metabolites are associated with obesity through short chain fatty acids, a byproduct of gut fermentation of complex carbohydrates and is mediated by lifestyle and geographic location.

*To test these hypotheses we will complete the following Specific Aims:*

- 1) Recruit 500 participants, ages 25-45, from each of 5 populations (total N = 2,500); measure AEE with accelerometry; collect 24-hour dietary recalls; assess fasting glucose/insulin, ghrelin, and adipocytokines (adiponectin, leptin).
- 2) Measure AEE using DLW in a random subset of 75 participants from each of the 5 populations at baseline (total n = 375).
- 3) Repeat AEE measurement with accelerometry on all participants at 24 months; repeat weight at 12 and 24 months and body composition at 24 months.
- 4) Examine the relationship between AEE and body composition within and among populations at baseline and at follow-up; assess inter-relations of AEE and diet, glucose, insulin, ghrelin and adipocytokines.
- 5) Measure serum 25(OH)D and intact parathyroid hormone (iPTH) levels in 500 adults from the 5 METS sites (total N=2,500) at baseline and determine associations with latitude, diet, physical activity, adiposity, blood pressure (BP), and biochemical risk factors for CVD (eg, insulin, glucose, adiponectin, leptin, cholesterol).
- 6) Examine the association between baseline serum 25(OH)D and iPTH levels and changes in body composition and blood pressure over 6.5 years of follow-up.
- 7) Repeat measurement of serum 25(OH)D and iPTH at third follow-up examination (approximately 3.5 years after baseline) and measure BMD using DXA in the available cohort.
- 8) Identify a metabolite profile that predicts progression to IGT/T2D in diverse black populations spanning the epidemiologic transition.
- 9) We hypothesize that the plasma metabolite profile at baseline (2009) will be significantly associated with changes in diabetic status over the same 6-year period (2009 to 2015), i.e. normal glucose tolerance (NGT) to IGT and/or T2D.  

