### C.2.2.2 Physical Activity and Weight Change

[figure not shown]
The Loyola-Ibadan Women's Study was initiated in 2000 to study the relationship between resting EE, AEE, and weight change in women from two contrasting social settings. In both metropolitan Chicago and rural Nigeria, women were enrolled in a longitudinal survey in which EE was measured at baseline using DLW, and weight and body composition were measured for 3 consecutive years (Table 3) [135]. Mean change in weight during the follow-up interval was 0.73 and 0.76 kg/y for the Nigerian and US women, respectively. Contrary to our hypothesis, no association was observed between activity EE at baseline and weight change in either site [136]. This result underscores our prior assertion that variation in AEE in free-living populations has not been convincingly shown to predict risk of obesity. Unfortunately, the sample size in this cohort is somewhat small, and we were limited to two sites.

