## D.4 Measurement Procedures

### D.4.1 Activity Energy Expenditure

Total daily EE is comprised of three components: resting EE, AEE, and thermic effect of food. In this study, we are most interested in AEE and its relationship to weight change and insulin sensitivity. AEE will be measured by two methods: accelerometers and DLW. All participants in each site will wear an activity monitor for 6-9 days, while a subset will undergo the DLW procedure as well. Our previous experience with measurement of EE indicates that both resting EE and AEE are very stable traits, with within-person correlations of 0.9 and 0.8 at intervals of 1-2 years, respectively [135]. For those participants in the DLW

[figure not shown]
subset, resting EE will be measured by indirect calorimetry, and thermic effect of food will be estimated as 10% of total daily EE. All methods are described below.

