There is controversy over the number of days of recording needed to adequately capture habitual activity levels; the suggested range is from 4 to 9 days [152]. We used the Spearman-Brown prophecy formula with calculated, site-specific intraclass correlation coefficients [157] to estimate the level of reliability achieved for a given number of days of monitoring in each site (Figure 7) [152]. Most studies use 0.8 as an acceptable level of reliability [152, 158-161]. For our data, all sites achieve this level with five days of monitoring (ie, excluding the first and last partial days of monitoring which are dropped from analysis), however the Seychelles are on the borderline. Given the practicality of six days of monitoring (i.e., participants will receive the monitor and return the monitor on the same day of the week), we have chosen to monitor all participants for six days (i.e., a total of 8 after taking the two partial days into consideration). With six days of monitoring, the expected level of reliability will be 0.83-0.92.

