Where  $T_{i1} = 0$ ,  $T_{i2}=12$ , and  $T_{i3}=24$  correspond to the three times at which weight will be measured for the  $i$ -th subject;  $X_i$ , and  $Z_i$  are potential confounders; and  $\Omega$  and  $\Psi$  are model parameters associated to the confounders. Confounders will include demographic variables and EI variables (e.g. total intake, percent calories from fat, etc). This approach corresponds to a multivariate nutrient density method suggested in the literature [73]. The effect of type of food most frequently consumed (e.g. vegetables, industrially processed foods, etc) will be accounted for by including dummy variables in our multivariate regression models. Note that the parameter  $\beta_{1i}$ , in the Level-1 equation, represents the weight change of the  $i$ -th subject. Thus, the Level-2 equation for this parameter models the dependence of weight change on AEE after adjusting for other covariates. A similar interpretation for the intercept parameter,  $\beta_{0i}$ , holds. In both instances site-specific factors could be included.

The multilevel approach can be extended to accommodate time-varying covariates, which we will apply to investigate the effect of changing AEE on weight change. In addition, the effect of AEE in the  $i$ -th subject ( $\Delta AEE_i$ ) on weight change will be assessed by replacing  $AEE_i$  in the Level 2 step of the multi-level analysis above by ( $\Delta AEE_i$ ).

Finally, one additional co-variate capturing exposure information will be created which will define the pattern of AEE. After examining the within-person distribution over the monitored days (eg, within-person SD) we will use both continuous and categorical transformations to characterize "consistent vs variable" patterns. Our pilot data suggest substantially more consistent patterns in Nigeria vs. the US and this may impact on the AEE-weight relationship.

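### The ΔAEE slope in the weight-change model will be attenuated, to roughly 15-70% of its true size at a stability of 0.8, and D.7.1.2 plans no correction for measurement error

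*Combined protocol and SAP*

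**What the plan says.** Accelerometry is done twice. Specific Aim 3 (Section A) says: "Repeat AEE measurement with accelerometry on all participants at 24 months". Table 5 agrees and shows DLW at baseline only, so any change in AEE is a difference of two accelerometer readings.

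D.7.1.2 plans two analyses of change. The first treats AEE as a time-varying covariate, "which we will apply to investigate the effect of changing AEE on weight change". The next sentence puts ΔAEE in place of AEE in the Level 2 equation. Neither mentions measurement error in the exposure.

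The monitoring period is justified in D.4.1.1: "We used the Spearman-Brown prophecy formula with calculated, site-specific intraclass correlation coefficients". At the 0.8 threshold, "all sites achieve this level with five days of monitoring", "however the Seychelles are on the borderline". Then: "With six days of monitoring, the expected level of reliability will be 0.83-0.92". These figures describe a single reading.

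D.4.1 calls resting EE and AEE very stable, "with within-person correlations of 0.9 and 0.8 at intervals of 1-2 years, respectively", so 0.8 is the AEE figure. It cites the same reference (no. 135) as the study of women in two settings in C.2.2.2, where "EE was measured at baseline using DLW, and weight and body composition were measured for 3 consecutive years".

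The only provision for exposure error is in the baseline analysis, D.7.1.1.1. It is a regression-dilution type of analysis that could be used if appropriate, and it is worded for noise in individual exposure levels.

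**The concern.** A difference of two noisy readings carries the error of both, while the stable part of the trait cancels. The more stable AEE is, the less true change there is to find and the larger the share of ΔAEE that is day-to-day noise. A reliability that serves well for a level can therefore be poor for a change.

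If ΔAEE is entered uncorrected, its slope is pulled towards zero. Two misreadings could follow. A small or null slope could be taken to show that changing one's activity has little bearing on weight. A weaker slope at one site could be taken for real heterogeneity when that site merely has lower reliability. The second matters because D.7.1.1.1 intends to use the repeat accelerometer data to explain weak or absent relationships at particular sites.

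**Working it through.** **Inputs.** Six-day reliability R = 0.83 to 0.92 across sites (D.4.1.1). Stability r = 0.8 over 1-2 years, one value for all sites (D.4.1). Assumptions: equal variances at the two visits, and errors independent of each other and of true AEE.

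**Reproducing the plan's figure.** A site at the borderline has five-day reliability 0.80. By Spearman-Brown its single-day ICC is 0.80/(5 − 4 × 0.80) = 0.444, and its six-day reliability is 6 × 0.444/(1 + 5 × 0.444) = 0.828. This matches the stated lower limit of 0.83. The 0.92 implies a single-day ICC of 0.657, which cannot be checked because the site values are in a figure that is not available.

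**Reliability of ΔAEE**, which is also the fraction of the true ΔAEE slope retained:

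- *A. If 0.8 is the observed correlation of two accelerometer readings*, it is (R − r)/(1 − r). At R = 0.83: 0.03/0.20 = 0.15. At R = 0.92: 0.12/0.20 = 0.60.
- *B. If 0.8 is the correlation of true AEE (ρ)*, it is R(1 − ρ)/(1 − Rρ). At R = 0.83: 0.166/0.336 = 0.49. At R = 0.92: 0.184/0.264 = 0.70.
- *C. If 0.8 was observed with DLW of reliability 0.90-0.95 (an assumed range)*, then ρ = 0.8/0.90 = 0.89 to 0.8/0.95 = 0.84. Formula B gives 0.35-0.44 at R = 0.83 and 0.56-0.65 at R = 0.92.
- *If observed accelerometer tracking is only 0.6 (assumed)*, formula A gives 0.23/0.40 = 0.58 and 0.32/0.40 = 0.80.

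A simulation of 400,000 subjects gave slope ratios of 0.151 and 0.602 for A, and 0.496 and 0.696 for B. Adjusting for baseline AEE left them essentially unchanged. The slope on the baseline level keeps a fraction R, that is 83-92%.

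**Fragility of the low end.** Under A at R = 0.83, the factor is (0.83 − 0.75)/0.25 = 0.32 at r = 0.75. At r = 0.85 it is (0.83 − 0.85)/0.15 = −0.13, which is impossible. The 0.15 rests on a gap of 0.03 between two rounded figures.

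**Contrast between sites.** Under B, with the same true stability everywhere, the ratio of the extremes is 0.697/0.494 = 1.4. Under A it is 0.60/0.15 = 4. But A then implies true-score correlations of 0.8/0.83 = 0.96 and 0.8/0.92 = 0.87, so it builds in less true change at the low-reliability site.

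**Power illustration.** Assume a true correlation of −0.15 between change in AEE and weight change (the size D.7.2 uses for a related correlation) and a two-sided 5% Fisher Z test. The observed correlation is the true one times the square root of the reliability.

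- One site, 400 completers (D.1.1): 85% without error, 56-71% at reliability 0.49-0.70, and 21% at 0.15.
- Pooled, 2,000 completers (D.7.1.1.1), reliability 0.15: observed correlation 0.15 × √0.15 = 0.058 in absolute value; 0.058 × √1,997 ≈ 2.60; power = Φ(2.60 − 1.96) ≈ 74%.

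**The case against.** - *The 15% figure is not the plan's own.* A reader might infer from 0.83 and 0.8 that 40-85% of ΔAEE is noise. That needs 0.8 to be an observed accelerometer correlation. D.4.1 does not say so, and the shared reference points to DLW in women at two settings. This stands: the range must be conditional.
- *A null is not assured.* A reader might infer that the instrument all but guarantees a null. It does not: the pooled analysis keeps about 74% power in the illustration even at the lowest reliability. Power is low within a site or for weaker effects.
- *The main hypothesis is hardly touched.* B.9 says that presence or absence of an association can be clearly interpreted, but it speaks of the study hypothesis. B.6 frames this as baseline activity against later weight change, and that slope keeps 83-92%. ΔAEE has no hypothesis or power calculation of its own. This stands and limits the point to a secondary analysis.
- *The site contrast is partly assumed.* A fourfold difference might be read off formula A. It imposes one observed correlation on every site, and the documents give no stability by site. The direction follows from the site range in reliability, but the size does not.
- *The quoted sentence concerns the time-varying covariate.* Its coefficient can mix between-person and within-person information, so the exact factor belongs to the ΔAEE model in the sentence after it.
- *A regression-dilution step exists.* It is optional, sits in the baseline section and is not specified for a change score. It softens the criticism without answering it.

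**Conclusion.** The concern holds for the ΔAEE model. As written, D.7.1.2 enters a change score without correction, and on every reading of the 0.8 that was tried its reliability is at most 0.70, against 0.83-0.92 for the level. The retained fraction of the true slope is roughly 15-70% at a stability of 0.8, with a fragile low end, and up to about 80% if observed tracking is 0.6. Attenuation is greater at sites with lower six-day reliability (Seychelles is the borderline one), by about 1.4-fold if true stability is equal and more under other assumptions.

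The consequence is a biased slope and weaker per-site power. The documents do not support a near-certain pooled null, a fourfold site difference as a finding, or any collapse of the baseline-AEE analysis.

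All of this assumes classical, independent error. Reliability taken from days within one monitoring period counts week-to-week and seasonal shifts as true change, so noise relative to habitual change in AEE could be larger than shown.

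**What to change.** In D.7.1.2:

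1. Define ΔAEE explicitly as 24-month minus baseline accelerometer AEE, and keep the naive estimate.
2. Estimate the reliability of ΔAEE at each site from the daily values at both visits, and report it beside every ΔAEE result.
3. Pre-specify an error-corrected estimate from a joint mixed model in which daily AEE values are repeated measures of latent AEE at 0 and 24 months, with day-to-day variance specific to site, and weight change depends on the latent change.
4. Do not simply divide the naive slope by the reliability where that is near zero. At 0.15 this multiplies the slope by 1/0.15 = 6.7, bootstrap draws can reach zero or below, and it is not equivalent to the latent-change model with covariates.
5. State that a null uncorrected ΔAEE slope, overall or at one site, is not evidence of no effect.

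The cost is SAP wording and extra programming. No new data are needed, since the monitors record by the minute and D.7.1.2 already uses the within-person SD across days. The downsides are wider confidence intervals and a correction that remains incomplete, because within-week variance misses week-to-week and seasonal variation.

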#### D.7.1.3 Comparison of Mean AEE Levels Among Sites

The 2 sample t-test will be used to compare means of the primary continuous variables, e.g., BMI, PA, weight, and height. Relevant co-variates will be identified from the within-site analyses and added using multivariable models [186, 190]. We recognize that some modifying factors within sites may not have the same significance across sites, and we will be very careful how variables are chosen for these analyses. Finally, we will test whether the regression slopes of the PA-BMI relationship varies significantly among any pair of sites (i.e., test for interaction).

The association between mean levels of AEE and mean levels of obesity/relative weight will be assessed using regression analysis, following a meta-regression type of approach. That is, mean AEE values will be regressed on mean obesity/relative weight values, weighting by the inverse of the squared standard error of the mean AEE values [191]. This is a widely-used approach in meta-analysis [192]. It is recognized that EI is an important potential confounder of the associations at the individual level. We will estimate the median (and other quantiles of the distribution) usual intake of nutrients (e.g. fat, percent fat) using methods developed by the ISU research group [179, 193] and include them in the meta-regression models.

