## D. EXPERIMENTAL DESIGN AND METHODS

### D.1 Project Overview

#### D.1.1 Participant Recruitment and Baseline Exam

Population-based samples, ages 25-45, will be drawn from communities in 5 countries: Nigeria, Seychelles, South Africa, Jamaica and the US; 500 per site, 2500 total. Based on our overall experience with

longitudinal studies, we experienced 2% annual attrition in Nigeria and 10% in the US site, we anticipate no more than 20% attrition by the 24-month examination, resulting in a final 'N' of at least 400 per site (Table 5).

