#### **D.7.1.1 Weight and Body Composition are Related to AEE at Baseline**

##### **D.7.1.1.1 AEE, Weight and Body Composition**

Two measures of AEE will be available. At baseline, we will have 500 participants/site with data from the accelerometer, inclusive of those who have both DLW and accelerometer (total N, all sites = 2500; 6 days

of monitoring). We will have data generated by DLW for 75 participants/site (total N, all sites = 375). The structure of the analysis will be similar with both exposure measures.

We anticipate that data for all the primary outcomes will not conform entirely to a normal Gaussian distribution. Using BMI, PAL and AEE data collected in previous studies in Maywood (n = 567) and Nigeria (n = 735), we examined the probability distributions. A formal test statistic was performed that combines kurtosis and skewness [180] as implemented in STATA with p-values less than 0.001, suggesting deviations from normality. Kernel density estimates of the BMI, AEE, and PAL distributions are depicted in Figure 7. After applying the ladder of power approach suggested by Tukey [181], we found that BMI, AEE and PAL for both sites appear to deviate from normality. Although no transformation is preferred after application of the ladder of powers method, two potential transformations are suggested by this approach, namely  $\log X$  and  $X^{-1}$ . Tukey's approach followed by formal testing will be carried out once data on all subjects in the study has been collected and a decision about data transformations has been made. Despite the lack of normality exhibited and corroborated by the statistical tests performed, a visual exploration of Figure 7 suggests only slight deviations from normality, mostly due to well-known skewness of these distributions. Thus, we anticipate the statistical methods that make use of normally distributed data will be appropriate to analyze these data. Of course, the degree of appropriateness of these methods will depend on their robustness to deviations from normality. If it is necessary, appropriate transformations will be carried out before statistical tests are performed.

**Figure 7.** Distribution estimates of main analysis variables BMI, AEE, and PAL in two sites: Maywood (US) and Nigeria.

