*Interactions between AEE and site:* Multiplicative interaction terms will be included in regression models to assess how much site modifies the association between AEE and the risk factor. We are fully aware of the lack of statistical power to test this type of hypotheses and thus results will be exploratory in nature. Thus, one might anticipate that anthropometric and AEE measures are stronger in low risk population samples than in the US. In addition, we will test whether the slope of the exposure-outcome relationships are influenced by the mean BMI of the population using multilevel regression models.

Questionnaire data on AEE will be summarized using methods previously developed [188]. Mean activity levels and prevalence of inactivity will be assessed in relation to objective measures of EE and the relevant outcome variables. As a sub-analysis we will describe types of activities reported to assess overall population patterns.

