## D.7.2 Power Analysis

A statistical justification for the selected sample size is provided for each aim of the study according to the suggested analytical plan. Sample size estimation for each of these hypotheses will be obtained, and the maximum number required to test them with sufficient power (80% or higher) will be selected.

- 1) PA is negatively related to percent body fat and CV risk factors in the study populations at baseline.

It has been previously estimated (cf. Preliminary Studies) that the correlation between PA, measured with DLW, and body composition is between -0.6 and -0.5. A correlation of -0.33 or smaller (larger in absolute value) will be detectable with 83% power and maximum probability of type I error alpha = 5% using a one-sided Fisher's Z test and 75 subjects per site [194].

- 2) PA is negatively related to change in body fat composition.

- a) *Physical Activity Measured by Accelerometer:*

PA, measured by the accelerometer, is associated with changes in body composition. For design purposes we will use the approach described above in the analysis section (see D.7.1.2. method 3). That is, two AEE groups will be formed by using the median AEE as the cut point. A method developed by Frison and Pocock [195] will be applied to compare mean changes between groups in a longitudinal analysis, adjusting for baseline values. In this method the following assumptions are made: the correlation between any 2 weight determinations is ~ 0.60 and the minimum acceptable difference between the means is 0.25 standard deviations (i.e., effect size equals 0.25) [186]. There will be one baseline measure of weight and two follow-up measurements. An analysis of covariance approach will be used to adjust for baseline values. Thus, to detect the pre-specified minimum difference with 90% statistical power we will need to accrue 460 subjects per AEE group (230 in the Low and 230 in the High group). We will accrue a total of 500 individuals per site in anticipation of a conservative total attrition rate of ~ 20%.

- b) *Physical Activity Measured by Doubly Labeled Water:*

The correlation between AEE and change in body composition is anticipated to be weaker (i.e., smaller in absolute value) than that observed between AEE and body composition at baseline. Data from previous studies (cf. Section C: Preliminary Studies) suggest that the association between AEE and body composition remains constant across studies.

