Although the study is not powered to test for differences in the association across sites (i.e., effect modification), we will undertake this task to ensure that large differences among the correlation coefficients do not exist. In addition, sites in which the correlation coefficient is deemed to be similar will be combined, and then comparisons of the correlations will be performed. For the sake of illustration, assume that 2 sites ( $n = 150$  individuals) are compared to other 2 sites ( $n = 150$  individuals). Thus, a two-sample, one-sided test of the correlations, assuming -0.4 versus -0.65, will yield over 91% power, whereas the power will be over 80% for comparison of -0.45 and -0.65, and between -0.35 and -0.6 the power is greater than 85%. Combining the data samples from all 5 sites and assuming constant

association will demonstrate a correlation between AEE and change in body composition of -0.15 or smaller (larger in absolute value) with over 83% power.

3) Mean levels of AEE are negatively related to mean levels of obesity/relative weight among the populations.

As previously demonstrated, sample sizes within sites will allow us to rule out correlations larger than 0.33 (absolute value), even when AEE is determined by DLW. Furthermore, we have estimated (cf. Preliminary Studies) that the within-site correlation between AEE and body composition of individual data could be as large as 0.6. We anticipate that the correlation between mean AEE levels and mean body composition will exceed 0.85. This estimate is justified in the following manner. A Fisher's Z-transformation 5%-significance test will have over 55% power to detect this correlation with 5 values corresponding to the 5 sites of the study. However, after dividing our samples by gender there will be 10 observations (2 X 5 countries), resulting in over 95% statistical power. Assuming an effective sample size of 7, to account for within-country correlations, the statistical power is 80%. Note that additional power will be gained when weighted linear regression methods are applied to estimate the correlation (slope) between AEE and body composition using meta-regression. Given the strong a prior hypothesis we can also compare mean AEE in the groups with the highest and lowest rates of obesity to test the ecological association.

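### Five sites are compared pair by pair with no overall test, stated alpha or multiplicity adjustment; if all five PA-BMI slopes are equal, two-sided 5% tests give a false slope difference about 26–29% of the time

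*Combined protocol and SAP*

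**What the plan says.** The comparison of sites is set out in D.7.1.3. For means: "The 2 sample t-test will be used to compare means of the primary continuous variables, e.g., BMI, PA, weight, and height". For slopes: "we will test whether the regression slopes of the PA-BMI relationship varies significantly among any pair of sites", followed by a parenthesis that calls this a test for interaction. The section states no significance level or sidedness for either comparison, puts no overall test ahead of them, and makes no adjustment for the number of pairs.

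The design (D.1.1) is: "Population-based samples, ages 25-45, will be drawn from communities in 5 countries", with "500 per site, 2500 total". The doubly labelled water subset has 75 per site (D.7.1.1.1).

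Three other places bear on how much weight these tests carry:

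- D.7.2 names a 5% level, but for other tests: "maximum probability of type I error alpha = 5% using a one-sided Fisher's Z test". Its illustration of a cross-site comparison is one-sided: "a two-sample, one-sided test of the correlations, assuming -0.4 versus -0.65, will yield over 91% power".
- D.7.2 also says that the study lacks power for differences in the association across sites. It nevertheless takes the association as constant in its pooled power calculation.
- D.7.1.1.2, on AEE-by-site interactions in the risk-factor models, says: "We are fully aware of the lack of statistical power to test this type of hypotheses and thus results will be exploratory in nature".

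**The concern.** A two-sample t-test can cover five sites only by taking them two at a time. The slope sentence, read literally, declares heterogeneity as soon as one of 10 pairs is significant. Ten looks at a nominal level, with no overall test, give a false alarm far more often than that level suggests.

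Slopes are where this matters. Whether the activity–obesity relation is common to the five populations is one of the things the study sets out to learn. A claim that two populations differ in that relation would be read as a substantive finding. If the relation is in fact common, the literal rule is a poor check of it.

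**Working it through.** **Is there a figure in the plan to reproduce?** The plan states no family-wise error rate for site comparisons. The nearest figures are the cross-site powers in D.7.2 (150 versus 150 participants), which show what level the plan has in mind. With Fisher's z for -0.40 versus -0.65:

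- (atanh 0.65 − atanh 0.40) / √(2/147) = (0.7753 − 0.4236) / 0.1166 = 3.015.
- One-sided 5%: Φ(3.015 − 1.645) = 91.5%, matching the plan's figure of over 91%.
- Two-sided 5%: Φ(3.015 − 1.960) = 85.4%, which does not match.

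The other two illustrations also agree one-sided (80.1% and 87.8%, against over 80% and over 85%). Two-sided they give 70.2% and 80.2%. An unadjusted 5% is therefore a reasonable assumption for D.7.1.3, but it remains an assumption. So does two-sided testing.

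**Inputs.** Five sites give 5 × 4 / 2 = 10 pairs. Two-sided 5% per pair is assumed, so the critical value is 1.96.

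**Chance of at least one false difference, all five sites equal.** The pairs share sites, so the independence formula 1 − 0.95^10 = 0.401 does not apply. With equal standard errors, the largest pairwise |z| exceeds 1.96 exactly when the studentised range of five exceeds 1.96 × √2 = 2.772:

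- P(range of 5 > 2.772) = **0.286**.
- With pooled degrees of freedom: 0.2856 at 500 per site and 0.2846 at 75 per site.
- Simulated two-sample t-tests, 400,000 runs: 0.284 (500 per site), 0.286 (400) and 0.286 (75).

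**Slopes with unequal standard errors** (relative values assumed, 400,000 runs each):

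| Relative standard errors, sites 1–5 | P(at least one false pair) |
|---|---|
| 1, 1, 1, 1, 1 | 0.286 |
| 1, 1.3, 0.8, 1.5, 0.7 | 0.277 |
| 1, 2, 3, 1, 0.5 | 0.256 |

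**Sensitivity to the assumptions.**

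- One-sided 5% tests, each in a direction fixed in advance: 0.303.
- Only some sites equal, chance of a false difference among those: four equal 0.203, three equal 0.122, two equal 0.050.

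**Does the all-equal case describe BMI means?** D.3.2 says that the sites were chosen for their spread in mean BMI. Taking the population means and SDs in Table 1, with 250 per sex per site (500 split equally by sex), z = difference / √((SD₁² + SD₂²)/250). For women in Nigeria versus Maywood this is (22.9 − 29.8) / √((6.0² + 8.1²)/250) = −10.8. In all, 15 of the 20 sex-specific pairs have expected |z| above 1.96. The all-equal case does not apply to BMI means.

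**After the change.** One 4-df test at 5% gives 5.0% under the all-equal case (simulated 0.050). The Tukey critical value for five groups is 2.728, and 2.728 / 1.960 = 1.39.

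**The case against.** The strongest reply is that the slope test may already be the right one. The parenthesis calls it a test for interaction, in the singular, and D.7.1.1.2 puts AEE-by-site terms into regression models. On that reading, any pair differing is simply the alternative hypothesis of one joint test, with a 5% error rate. This reading is possible. But the sentence as written refers to pairs, and a plan that can be read as either 5% or about 29% needs one more sentence.

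The second reply is that these comparisons are secondary. D.7.1.1.2 calls AEE-by-site results exploratory, and D.7.2 concedes low power for differences in association. Both points lower the weight of the concern. They do not remove it: the exploratory label is attached to the risk-factor models and is not repeated in D.7.1.3, and low power concerns missed differences, not false ones. Hypothesis 3, on population means, is assessed mainly by the meta-regression, which this point leaves untouched.

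Third, equality of all five slopes is not the plan's only expectation. D.7.2 works with a constant association, stated for activity and body composition, but D.7.1.1.2 allows that relations may be stronger in low-risk populations. If only four or three sites share a slope, the error among them is 20% or 12%.

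A reader might infer three stronger things that the documents do not support:

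- **That this test decides which sites are pooled.** D.7.2 describes combining sites whose correlation coefficients are judged similar. D.7.1.3 attaches no decision to the PA-BMI slope test.
- **That the error applies to every variable named for the t-tests.** It needs all five sites to be equal on that variable, which is contradicted for BMI.
- **That the ten sex-by-site groups are also compared pairwise.** In D.7.2 they are ten data points for a single correlation, and D.7.1.3 plans no pairwise tests among them.

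**Conclusion.** The concern holds in limited form. D.7.1.3 describes pairwise comparisons of five sites without a stated alpha, sidedness, overall test or adjustment. If the 10 slope pairs are each tested two-sided at 5% and all five slopes are equal, at least one false difference appears about 26–29% of the time: 28.6% with equal standard errors, less in the unequal patterns tried. The 5% level is inferred from D.7.2, two-sided testing is assumed, and the unequal standard errors are illustrative. The figure should not be applied to BMI means. Because these are secondary comparisons with acknowledged low power, this is a modest gap in specification, not a threat to the main hypotheses.

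**What to change.** In D.7.1.3:

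1. State that heterogeneity of the PA-BMI slope is judged by one joint 4-df AEE-by-site interaction test, at a stated two-sided alpha.
2. Replace the two-sample t-tests by one 4-df test of site for each variable. For BMI this test will almost certainly reject, so it screens out little there; its use is for variables on which equality is plausible.
3. Report pairwise contrasts as descriptive follow-up with confidence intervals. The joint test protects only the case where all sites are equal, so Tukey-Kramer intervals are a reasonable option, not a requirement.
4. Say whether the exploratory status given to AEE-by-site results in D.7.1.1.2 also covers these tests, and that a non-significant joint test is not evidence of a common slope, given the low power conceded in D.7.2.

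The cost is a few sentences in the analysis plan; no new data or participants are needed. If Tukey-Kramer intervals are used, pairwise intervals become about 39% wider (2.73 in place of 1.96).
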